2.2 Secondary objectives

- 2.2.1 To determine the efficacy of early integrated palliative care (PC) on other patient reported outcomes in patients with newly diagnosed incurable lung or non-colorectal gastrointestinal cancer, by assessing the endpoints detailed in Section 11.4.1.1.
- 2.2.2 To determine the efficacy of early integrated palliative care (PC) on family caregiver reported outcomes in those with newly diagnosed incurable lung or non-colorectal gastrointestinal cancer, by assessing the endpoints detailed in Section 11.4.1.2.
- 2.2.3 To assess the impact of early, integrated PC on quality of EOL care and resource utilization in patients with newly diagnosed incurable lung or non-colorectal gastrointestinal cancer by assessing the endpoints detailed in Section 11.4.1.3.
- 2.2.4 To determine concordance between patient and family caregiver report of prognosis/curability.

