9.0 MEASURES

Demographics: All study participants will complete a demographic questionnaire (see Appendix III for patient, Appendix IV for family caregiver) at the time of baseline data collection detailing their age, sex, race, ethnicity, religion, relationship status, education level, annual household income, and living situation (specify number of dependent children living at home). Family caregivers will also specify their relationship with the patient, living situation (specify number of dependent children living at home) and employment status.

QOL-Patient: To assess quality of life over time in study patients, we will use the Functional Assessment of Cancer Therapy (FACT) Questionnaires, which have been validated for use in multiple care settings and with diverse tumor types. The FACT consists of four subscales assessing well-being across four domains (physical, functional, emotional and social) during the prior seven days. Additional questions specific to cancer symptoms will be added to the measure for each tumor type, including lung (FACT-L), esophageal and gastric (FACT-E), and hepatic, biliary, and pancreatic (FACT-Hep) – See Appendix III.⁵⁸⁻⁶¹ Patients will complete this questionnaire at baseline, 6, 12 and 24 weeks.

QOL-Family caregiver: We will use short-form health survey (SF-36) to assess change in health-related QOL over time in family caregivers (see Appendix IV).⁶² The SF-36 measures eight domains of health-related quality-of-life: physical functioning, role limitations due to physical health, bodily pain, general health perceptions, vitality, social functioning, role limitations due to emotional health, and mental health. Family caregivers will complete this questionnaire at baseline, 6, 12 and 24 weeks.

Mood: We will use the Hospital Anxiety and Depression Scale (HADS) to assess symptoms of depression and anxiety in all study participants (see Appendix III for patient, Appendix IV for family caregiver).⁶³ The HADS is a 14-item questionnaire that contains two 7-item subscales assessing depression and anxiety symptoms during the past week. Scores on each subscale range from 0 to 21, with a cutoff of 8 or greater denoting clinically significant depression or anxiety symptoms. Patients and family caregivers will complete questionnaire at baseline, 6, 12 and 24 weeks.

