11.3 Statistical Design and Analysis for the Primary Endpoint

11.3.1 Primary Endpoint

The total scores of FACT-G will be calculated using the accompanying scoring algorithms. They will be further converted into a 0-100 quality of life scale for standardization. Change in FACT-G scores from baseline to 12 weeks between study arms will be the primary endpoint for this study. The disease-specific questions (additional concern) of FACT-L, FACT-E or FACT-Hep will be summarized in a descriptive manner between study arms.

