11.4 Supplementary Analysis Plans

11.4.1 Secondary Endpoints

11.4.1.1 The efficacy of early integrated palliative care (PC) on patient reported outcomes in patients with newly diagnosed incurable lung or non-colorectal gastrointestinal cancer will be assessed by analyzing:

1. Change in QOL on the FACT over time
2. Rate of depressive symptoms as per HADS at 12 weeks and over time
3. Rate of anxiety symptoms as per HADS at 12 weeks and over time
4. Change in illness understanding over time

11.4.1.2 The efficacy of early integrated palliative care (PC) on family caregiver reported outcomes in those with newly diagnosed incurable lung or non-colorectal gastrointestinal cancer will be assessed by analyzing:

1. Change in QOL on the SF-36 over time
2. Rate of depressive symptoms as per HADS at 12 weeks and over time
3. Rate of anxiety symptoms as per HADS at 12 weeks and over time
4. Change in illness understanding over time

11.4.1.3 The impact of early, integrated PC on quality of EOL care and resource utilization in patients with newly diagnosed incurable lung or non-colorectal gastrointestinal cancer will be assessed by analyzing:

1. Rate of referral, enrollment and length of stay on hospice
2. Location of death
3. Number of hospital and ICU admissions and days
4. Chemotherapy and radiation administration
5. Overall survival

11.4.1.4 Concordance between patient and family caregiver report of prognosis/curability.

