- 11.4.2.3** To assess differences in quality of EOL care, we will use Fisher's exact test to determine the association between the composite EOL care measure categories and study arm and a comparison of rates between the groups based on the risk difference and relative risk. To assess the difference in resource utilization, we will also compare days on hospice and in the hospital and ICU using the Mann-Whitney U test. To compare patient survival, we will use Kaplan-Meier estimates, testing the difference between the curves with the log-rank test.
- 11.4.2.4** To assess the concordance between patient and family caregiver report of prognosis/curability, we will analyze each of the primary and secondary endpoints using the matched-pair subset. Simple tests such as paired *t*-test, Wilcoxon signed-rank test, and generalized linear models for matched pair data will be utilized.

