	Extremely Helpful	Very Helpful	A Little Helpful	Not at all Helpful
Making decisions about treatment				
Preparing for the future				
Maintaining hope				
Coping with the disease				
Overall, how helpful has knowing about prognosis been for you?				

10. How would you describe your current medical status? *Please check one.*

Relatively healthy
 Relatively healthy and terminally ill
 Seriously ill and not terminally ill
 Seriously ill and terminally ill

11. How likely do you think it is that you will be cured of cancer? *Please check one.*
 - Extremely likely (more than a 90% chance of cure)
 - Very likely (75-90% chance of cure)
 - Moderately likely (50-74% chance of cure)
 - Somewhat likely (25-49% chance of cure)
 - Unlikely (10-24% chance of cure)
 - Very unlikely (less than 10% chance of cure)
 - No chance (0% chance of cure)

12. Have you and your oncologist discussed any particular wishes you have about the care you would want to receive if you were dying? *Please check one.*
 - Yes
 - No

13. If you had to choose, would you prefer 1) a course of treatment that focused on extending life as much as possible, even if it meant more pain and discomfort, or 2) a plan of care that focused on relieving pain and discomfort as much as possible, even if that meant not living as long? *Please check one.*
 - Extend life as much as possible
 - Relieve pain as much as possible
 - Don't know

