Making decisions about treatment				
Preparing for the future				
Maintaining hope				
Coping with the disease				
Overall, how helpful has knowing about prognosis been for your loved one?				

10. How would you describe your loved one's current medical status?

Relatively healthy
 Relatively healthy and terminally ill
 Seriously ill and not terminally ill
 Seriously ill and terminally ill

11. How likely do you think it is that your loved one will be cured of cancer? *Please check one.*
 Extremely likely (more than a 90% chance of cure)
 Very likely (75-90% chance of cure)
 Moderately likely (50-74% chance of cure)
 Somewhat likely (25-49% chance of cure)
 Unlikely (10-24% chance of cure)
 Very unlikely (less than 10% chance of cure)
 No chance (0% chance of cure)

12. Has your loved one and their oncologist discussed any particular wishes about the care they would want to receive if they were dying? *Please check one.*
 Yes
 No

13. If your loved one had to choose, would they prefer 1) a course of treatment that focused on extending life as much as possible, even if it meant more pain and discomfort, or 2) a plan of care that focused on relieving pain and discomfort as much as possible, even if that meant not living as long? *Please check one.*
 Extend life as much as possible
 Relieve pain as much as possible
 Don't know

Important Reminders When Discussing the Study:

1. Palliative care is NOT hospice or end-of-life care. The goal of palliative care is to help patients live as well as they can for as long as they can.
2. The palliative care team will not “force” people to talk about death and dying or other topics they are not ready to discuss.
3. Patients’ cancer treatment or treatment clinical trials will NOT be impacted by their participation in this study.
4. Patients without willing family members are still able to participate.

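### Section 11.4.2.4 assesses patient–caregiver concordance on prognosis through every primary and secondary endpoint, and names neither the PTPQ items that measure it nor an agreement statistic

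*Combined protocol and SAP*

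**What the plan says.** Section 2.2.4 states the objective: "To determine concordance between patient and family caregiver report of prognosis/curability". Section 11.4.1.4 lists the matching endpoint on its own: "Concordance between patient and family caregiver report of prognosis/curability".

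Section 11.4.2.4 is the only text that gives an analysis for this objective. It restates the aim and then says "we will analyze each of the primary and secondary endpoints using the matched-pair subset". On method it adds: "Simple tests such as paired *t*-test, Wilcoxon signed-rank test, and generalized linear models for matched pair data will be utilized". It gives no instrument, item, time point or measure of agreement.

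The primary endpoint in 11.3.1 is a patient score: "Change in FACT-G scores from baseline to 12 weeks between study arms will be the primary endpoint for this study". Caregiver quality of life uses a different instrument (section 9.0): "We will use short-form health survey (SF-36) to assess change in health-related QOL over time in family caregivers".

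The PTPQ is given to both members at weeks 6, 12 and 24, and not at baseline (sections 6.2 and 6.3). Its item 11 asks the patient "How likely do you think it is that you will be cured of cancer" (Appendix III) and the caregiver "How likely do you think it is that your loved one will be cured of cancer" (Appendix IV).

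**The concern.** The endpoint is narrow and the rule for analysing it is broad. Most of the endpoints that the rule takes in have no value from the other member of the pair, or have nothing to do with prognosis. The items that carry the stated endpoint are covered only by implication, as part of illness understanding.

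Two things are at stake. First, the analyst must choose the concordance variable and the visit, possibly after seeing the data. Second, paired tests of location could be reported as evidence on concordance when they do not measure it.

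**Working it through.** The plan states no figure on this point, so the check is a count, followed by a comparison of the two questionnaire versions.

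**Endpoints taken in by the rule.** These are the primary endpoint (11.3.1) and the lists in 11.4.1.1 to 11.4.1.3. The concordance endpoint is left out, because including it would make the rule circular. The total is 1 + 4 + 4 + 5 = 14. Each is classified from the data schedules in sections 6.2, 6.3 and 6.4, the survival follow-up in 7.4 and the descriptions in 9.0.

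| Endpoint | Number | Same instrument in the other member? | Measures prognosis? |
|---|---|---|---|
| FACT-G change at week 12 (primary) | 1 | No | No |
| Patient FACT over time | 1 | No | No |
| Patient HADS depression, anxiety | 2 | Yes | No |
| Patient illness understanding (PTPQ) | 1 | Yes | Yes |
| Caregiver SF-36 | 1 | No | No |
| Caregiver HADS depression, anxiety | 2 | Yes | No |
| Caregiver illness understanding (PTPQ) | 1 | Yes | Yes |
| Hospice, place of death, hospital/ICU use, chemotherapy/radiation, survival | 5 | No | No |

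- No same-instrument counterpart: 1 + 1 + 1 + 5 = 8 of 14 (57%).
- Not a measure of prognosis: 14 − 2 = 12 of 14 (86%).

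**Sensitivity of the count.**
- Counting each of the three shared measures once leaves 14 − 3 = 11 endpoints. Of these, 8 (73%) have no counterpart and 10 do not measure prognosis.
- If FACT and SF-36 were accepted as counterparts despite their different scales, 8 − 3 = 5 of 14 would lack one. The 12 of 14 that do not measure prognosis would not change.

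**Which PTPQ items fit.** The questionnaire has 13 items. Items 10 and 11 ask each respondent for a personal judgement of the patient's medical status and chance of cure. The response options are the same in both versions: four categories for item 10 and seven ordered categories for item 11. Several other caregiver items, such as 1, 3, 5 and 13, ask the caregiver to report the patient's preferences or goals. Pairing those would measure how well the caregiver knows the patient's views, which is a different quantity.

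**Why location tests do not measure agreement.** A paired t-test or signed-rank test asks whether patients and caregivers differ systematically in one direction. It does not ask whether the two members of a pair give the same answer. For illustration, assume 300 complete pairs (section 11.2.1 expects about 300 caregivers), a seven-level item, and patient and caregiver answers that are independent and uniform. In 1,000 simulated data sets, weighted kappa (squared weights) averaged 0.00, meaning no agreement beyond chance. The paired t-test and the signed-rank test each rejected in 4.9% of runs. A complete lack of concordance would therefore usually appear as no significant difference. The number of pairs and the uniform distribution are assumptions, not figures from the plan.

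**The case against.** The strongest reply is that the rule is too wide but does not replace the endpoint. Illness understanding is a listed secondary endpoint for patients (11.4.1.1) and caregivers (11.4.1.2). Section 11.4.2.1 analyses the PTPQ item by item, and 11.4.2.2 does the same for caregivers. Items 10 and 11 are therefore within the matched-pair analysis, and 11.4.2.4 opens with the right aim. This stands. A reader might infer that objective 2.2.4 would get no relevant analysis at all, but the documents do not support that. The defect is that the relevant items are not singled out.

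A second reply is that the matched-pair subset may simply mean patients with an enrolled caregiver, so that nobody intends to pair survival or FACT-G with a caregiver value. The wording allows this. It removes the oddity of unpaired endpoints, but repeating other analyses in that subset is still not an assessment of concordance.

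A reader might also add up paired tests over all shared measures and visits and predict a number of false positives. The documents do not support that either. The plan fixes no such set of tests, and PTPQ items 3 and 4 are unordered lists to which the named t-test and signed-rank test do not apply. Any such prediction would also assume that every null hypothesis is true. Section 11.4.2 already calls significant findings from these analyses exploratory and makes description the basis of most of them.

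Finally, choosing items 10 and 11 is a judgement. Items 3 and 4 offer cure as a treatment goal, and items 5 to 8 mention prognosis. That is fair, and it is a reason for the plan to state its choice.

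**Conclusion.** The point holds as a minor one. The only analysis rule for the concordance objective does not fit its endpoint: 8 of 14 listed endpoints have no same-instrument counterpart and 12 of 14 do not measure prognosis. The PTPQ items that do fit are inside the rule but not named, and no agreement measure is given.

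The 8 of 14 depends on treating FACT and SF-36 as not interchangeable. The 12 of 14 does not, and is the firmer figure. The weakness of the location tests follows from what they test; the simulation only illustrates it.

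The consequence is limited. The endpoint is outside the gatekeeping sequence and exploratory. The primary analysis, the sample size and data collection are untouched.

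**What to change.** In 11.4.2.4, replace the reference to all primary and secondary endpoints with wording such as: *the paired patient and caregiver responses to PTPQ item 11 (likelihood of cure; main concordance variable) and item 10 (medical status), at weeks 6, 12 and 24, in pairs where both responded*.

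In the same section, state the agreement measure, with a confidence interval: for example weighted kappa for item 11, whose categories are ordered, and kappa or percent agreement for item 10. The paired tests may be kept to describe a systematic difference between patients and caregivers, but not as the measure of concordance.

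Any matched-pair analysis of HADS or other endpoints can stay as a separately labelled exploratory analysis.

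The cost is two or three sentences in the analysis plan, written before the paired data are examined. No new data are needed and participants have no extra burden, because both items are already collected from both members at the same visits.

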Prognosis and Treatment Perceptions Questionnaire: [name] has evaluated the content validity and readability of a thirteen-item Prognosis and Treatment Perception Questionnaire (PTPQ) to assess perceptions of prognosis, goals of treatment, and quality of communication with oncologists among patients with incurable cancer (see Appendix III for patient, Appendix IV for family caregiver). The PTPQ was recently used to assess illness and prognostic understanding in patients with advanced gastrointestinal cancers.⁶⁴ We will administer the PTPQ to patients and their family caregivers in order to assess (1) illness knowledge and understanding; (2) communication and perceptions regarding prognosis and goals of care; and (3) discussions and preferences regarding EOL care. Patients and family caregivers will complete this questionnaire at 6, 12, and 24 weeks.

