11.4.2 Secondary Analysis

We will adopt the gatekeeping procedure for the primary analysis of efficacy of early PC on patient reported outcomes, the secondary analysis of efficacy of early PC on family caregiver reported outcomes, and the secondary analysis of impact of early PC on quality of EOL care and resource utilization. Therefore, they will be tested at the 5% significance level in sequence, and the subsequent analysis (hypothesis testing) will only be carried out if the previous analysis is statistically significant. Otherwise, subsequent analysis will be descriptive in nature. Multiplicity will not be adjusted for other secondary analyses, hence, statistically significant findings from secondary analyses are exploratory in nature and therefore shall be interpreted as such. Descriptive statistics and graphical approaches will form the basis for most secondary analyses.

- 11.4.2.1** To assess the changes in QOL over time among patients, generalized linear model with repeated measures will be used for comparison between treatment arms. To compare rates of psychological distress between treatment arms, we will transform the HADS score into a dichotomous outcome with categories reflecting the presence or absence of clinically significant depression and anxiety. We will then use generalized linear models with repeated measures to assess the association between the presence of depression/anxiety and study arm, using risk difference and relative risk to compare proportions between the study arms. To compare the illness understanding, we will analyze each item of the PTPQ separately using the appropriate test to determine the significance of the between-group differences. To assess additional measures of family caregiver perceptions of quality of death, we will employ the Jonckheere-Terpstra test, which is appropriate for contingency tables with ordinal data.
- 11.4.2.2** To assess the changes in QOL among family caregivers, we will use the similar approach as for QOL among patients. Change in the total score and subscales will be compared with generalized linear models with repeated measures. Analysis of psychological distress and illness understanding will be the same as above.

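### The concordance analysis in Section 11.4.2.4 names no measure of agreement; the two simple tests it names detect a shift between patient and caregiver, which is a different question

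*Combined protocol and SAP*

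**What the plan says.** Section 2.2.4 sets the objective: "To determine concordance between patient and family caregiver report of prognosis/curability". Section 11.4.1.4 repeats it as an endpoint and attaches no statistic, questionnaire item or visit.

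Section 11.4.2.4 is the only analysis text for it. For this purpose, it says, "we will analyze each of the primary and secondary endpoints using the matched-pair subset". It then gives the paired t-test as an example of a simple test, followed by "Wilcoxon signed-rank test, and generalized linear models for matched pair data will be utilized". No outcome, link or estimand is given for the models. Neither percent agreement nor a kappa is named.

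Two general statements in Section 11.4.2 also apply: "Descriptive statistics and graphical approaches will form the basis for most secondary analyses", and "statistically significant findings from secondary analyses are exploratory in nature".

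Suitable data are already collected. Item 11 of the Prognosis and Treatment Perceptions Questionnaire (PTPQ) asks patients "How likely do you think it is that you will be cured of cancer" (Appendix III). The caregiver version (Appendix IV) puts the same question about the patient, with the same seven answer levels. Section 9.0 gives the timing: "Patients and family caregivers will complete this questionnaire at 6, 12, and 24 weeks".

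**The concern.** Concordance is a question about agreement: how often, or how closely, do the two members of a pair give the same answer? The paired t-test and the signed-rank test ask instead whether the within-pair differences centre on zero. Pairs can disagree widely while the differences cancel, and pairs can agree almost always while the few differences all point one way.

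If only those two tests were run, the objective would be reported without an estimate of concordance. A non-significant p-value could be misread as agreement, and a significant one as poor agreement. With item, visit and statistic all open, the choice among 13 PTPQ items and three visits could also be made after the data are seen.

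The endpoint wording has a second, smaller problem. Taken literally it covers measures that only one member of the pair has, so no within-pair comparison can be made on them.

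**Working it through.** The plan states no figure for concordance, so there is none to reproduce. The check is logical, with a numerical illustration.

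**1. What each quantity measures.** Let d be the caregiver's level minus the patient's level. The paired t statistic is mean(d) / (SD(d)/√n). The signed-rank test asks whether positive and negative d balance. Exact agreement is the proportion of pairs with d = 0. A mean of zero is compatible with almost any level of agreement.

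**2. Inputs.** Seven ordered levels come from PTPQ item 11 in both versions. The 300 pairs are the caregiver enrolment estimate in Section 11.2.1. The 150 pairs are an assumed lower figure (see step 6). The answer frequencies, also assumed, are 0.10, 0.10, 0.15, 0.15, 0.15, 0.20, 0.15. Tests are two-sided at 5%.

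**3. Three cases.** A shift that would leave the scale stays at the end level.
- A, independent answers: agreement = 2×0.10² + 4×0.15² + 0.20² = 0.150.
- B, 6% shifted up one level and 6% down: agreement = 0.88 + 0.06×0.15 + 0.06×0.10 = 0.895. After capping, 5.1% differ upward and 5.4% downward.
- C, 12% shifted up only: agreement = 0.88 + 0.12×0.15 = 0.898.

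The expected t at 300 pairs is 0 in A, −0.003/(0.324/√300) = −0.16 in B, and 0.102/(0.303/√300) ≈ 5.8 in C.

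Results from 10,000 simulated trials per case:

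| Case | Agreement | Significant at 300 pairs (t / signed-rank) | Significant at 150 pairs (t / signed-rank) |
|---|---|---|---|
| A | 15.0% | 5.3% / 5.3% | 4.9% / 5.0% |
| B | 89.5% | 5.5% / 5.5% | 5.2% / 5.2% |
| C | 89.8% | 100% / 100% | 100% / 100% |

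The tests do not separate A from B, which differ greatly in agreement. They do separate B from C, where agreement is nearly the same.

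**4. Percent agreement does separate A from B.** The middle 95% of simulated estimates is 11–19% against 86–93% at 300 pairs, and 9–21% against 84–94% at 150.

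**5. Kappa depends on its weights.** In case B it is 0.986 with quadratic weights, 0.952 with linear weights and 0.877 unweighted. With 30% shifted up and 30% down, agreement falls to 0.40 + 0.30×0.15 + 0.30×0.10 = 0.475. Kappa is then 0.93 quadratic, 0.76 linear and 0.38 unweighted. Quadratic weights largely overlook one-level disagreement, so the weights must be fixed in advance and exact agreement is the safer lead estimate.

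**6. Pairs and precision.** Section 11.2.1 gives 20–30% missing for the primary patient-reported measures. If that rate also held for the PTPQ, patients alone would reduce 300 pairs to 300×0.80 = 240 or 300×0.70 = 210. If caregivers matched it independently, 300×0.64 = 192 or 300×0.49 = 147 would remain. The 95% half-width for agreement is 1.96×√(p(1−p)/n):

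| Pairs | p = 0.15 | p = 0.50 | p = 0.90 |
|---|---|---|---|
| 300 | 4.0 points | 5.7 | 3.4 |
| 150 | 5.7 | 8.0 | 4.8 |
| 75 (one arm of 150) | 8.1 | 11.3 | 6.8 |

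**7. Which endpoints can be paired.** FACT is completed by patients only (Section 6.2) and SF-36 by caregivers only (Section 6.3). End-of-life care, resource use and survival belong to the patient (Section 11.4.1.3). HADS and PTPQ are completed by both, and HADS is not a report of prognosis.

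**The case against.** The strongest reply is that the plan leaves room for the right analysis. The simple tests are offered as examples, a matched-pair model can be set up with agreement as its outcome, and Section 11.4.2 makes descriptive statistics the basis of most secondary analyses. Percent agreement is such a statistic. All of this stands. A reader might infer that the objective cannot be met, or that no concordance estimate will be reported; the documents do not support either. What remains is that permission is not specification: no agreement measure, item or time point is named, and the two tests that are spelled out answer another question.

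Section 11.4.2.1 plans to analyse PTPQ items separately, and 11.4.2.2 extends this to caregivers. Those are comparisons between arms, so they show item-level work is intended but do not supply a within-pair measure.

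The endpoint sentence could also be read as repeating the main analyses among patients who have a caregiver in the study. That can be done, but it is not an analysis of concordance.

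It is also fair to say that the simulation illustrates a definition: about 5% rejection follows whenever the mean shift is null or nearly so. It shows the size of the gap and is not needed to establish it.

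**Conclusion.** The point holds as a gap in specification. Of the methods named, the two simple tests measure shift, and the matched-pair models are not specified well enough to supply an agreement estimate. That does not depend on the assumed answer frequencies. The percentages in the illustration do, because the documents give no joint distribution of patient and caregiver answers.

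The consequence is small. The analysis is exploratory and outside the gatekeeping sequence. The primary result, the significance level and the sample size do not depend on it. A reader might infer that the trial's efficacy conclusions are at risk, and nothing in the documents supports that.

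Two limits apply to the figures. The 300 pairs are an upper bound, because both members must answer. No general precision is claimed for kappa, since it varies too much with the assumed pattern of disagreement.

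**What to change.** Rewrite Section 11.4.2.4 along these lines:

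> Concordance will be assessed on PTPQ item 11 (likelihood of cure; seven identical levels in both versions) in pairs where both members answered. Week 12 is the main time point; weeks 6 and 24 are supportive. Percent exact agreement with a 95% confidence interval is the lead estimate. A kappa with weights stated in advance (unweighted or linear and, if wanted, quadratic) and the number of complete pairs will be reported beside it, overall and descriptively by arm. The signed-rank test and any matched-pair generalized linear model will describe the direction of disagreement only, unless the model is specified with agreement as its outcome.

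Replace the reference to all primary and secondary endpoints with measures that both members complete. Report any paired HADS comparison as a within-pair difference and not as concordance on prognosis. A between-arm test of agreement is not needed, because the objective does not ask for one.

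The cost is SAP wording and a little programming, with no new data. Precision is limited: about ±3 to 8 points for exact agreement with an assumed 150 to 300 complete pairs, and wider by arm. Pairs are likely to be fewest at week 24, since Section 6.2 does not require questionnaires once the patient is in hospice. That is one reason to lead with week 12, which also matches the time point of the primary endpoint.
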